7.2. Discontinuation of Subjects from Study Participation

Subjects will be informed that they are free to withdraw from the study at any time and for any reason. The PI may remove a subject from the study if, in the PI's opinion, it is not in the best interest of the subject to continue the study. Subjects may be discontinued due to a change in compliance with an inclusion/exclusion criterion that is clinically relevant and affects subject safety, occurrence of AEs, occurrence of pregnancy, or administration of non-permitted concomitant medication that might affect subject safety or study assessments/objectives. In addition, for any AEs noted, the PI will determine whether there is impact, or a potential for impact, on subject safety or study assessments/objectives, and will remove such subjects. Subjects will be discontinued due to clinically relevant changes in a subject's status related to Inclusion and Exclusion criteria that significantly affect subject safety or study integrity, development of pregnancy, or necessary administration of non-permitted concomitant medications that might affect subject safety or study assessments/objectives. Notification of discontinuation will be made immediately to the sponsor Medical Monitor or designee. In case of premature discontinuation of study participation, efforts will be made to perform all final EOT and EOS visits/assessments. The date the subject is withdrawn from the study and the reason for discontinuation will be recorded on the subject's Case Report Form (CRF). All withdrawn subjects will be followed until resolution of any AEs or until any unresolved AEs are judged by the PI to have stabilized.

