| Exploratory Biomarker 1, 2, 3 | | | X | X | X | X | X | X | X | X | X | X | X | X | |
| Aldafermin/placebo in clinic self-administration ^[t] | | | X | X | X | X | X | X | X | X | X | X | | | |
| Dispense aldafermin and diary | | | X | X | X | X | X | X | X | X | X | | | | |
| Dispense rosuvastatin ^[u] and diary | | | | X | X | X | X | X | X | X | X | | | | |
| Medication compliance | | | | X | X | X | X | X | X | X | X | | | X ^[v] | |
| Lipid management | | | | X | X | X | X | X | X | X | X | X | X ^[w] | X ^[w, x] | |

^[a] There must be a minimum of 14 days (2 weeks) between Day -56 and Day -42 Screening Visits to allow for adequate separation of liver function testing prior to randomization in order to evaluate worsening liver function, per Exclusion #7. If liver function tests are repeated to verify eligibility criteria have been met, there must be a minimum of 14 days (2 weeks) between the Day -42 visit and any unscheduled visit. The screening window may be increased up to 16 weeks (112 days) to obtain all screening assessments, with Medical Monitor approval.

^[b] Acceptable window from Week 2 through Week 6, and Week 54 (Week 58 if needed) is ±3-days. Visit window from Weeks 12 through 48 is ± 7 days. Visit window for Week 49 is +3 days.

^[c] During screening, sites will complete; i) AUDIT-C alcohol consumption questionnaire and, ii) document subject- reported alcohol consumption to confirm whether amounts are within protocol defined limits, and iii) PEth level ≥200 ng/mL (refer to exclusion criteria #18, 20).

^[d] Subjects should maintain their normal level of physical activity, diet, and lifestyle throughout the entire study.

^[e] BMI will be calculated with height obtained at Screening.

^[f] Gadolinium-enhanced MRI and multiphasic CT imaging must not have any nodules with LI-RADS ≥2. If nodules/lesions discovered on ultrasound that have not been previously defined by MRI or CT as clearly benign or LI-RADS <2, follow-up imaging with MRI or CT must be conducted for eligibility.

^[g] FibroScan® (transient elastography (VCTE™) or ultrasound attenuation rate (CAP™) should be collected at Screening Day -56, Week 24, and Week 48 at sites with available technology.

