[r] For subjects participating in the optional PK sub-study, blood samples will be collected when the subjects dose themselves in the clinic on Day 1 and Week 48 at pre-dose, and post-dose at 0.5, 1, 2, 4, 6, 8, 12, and 24 hours. The window for sample collection for the pre-dose through 4 hours is ± 5 minutes, 6-12-hour time points is ± 30 minutes. The window for sample collection for the 24-hour time points is -2 hours.

[s] A single buccal swab sample for PNPLA3/other genetic biomarkers will be collected pre-dose on Day 1.

[t] Subjects will be instructed to self-inject aldafermin/placebo in the abdomen at a similar time each day. Subjects will not self-inject aldafermin/placebo at home on clinic visit day.

[u] Rosuvastatin will be dispensed at Weeks 2, 6, 12, 18, 24, 30, 36, and 42 visits and subjects will be provided further dosing instruction based on their ASCVD risk assessment, prior statin history (statin naïve or statin experienced), and LDL-C levels or LDL reduction levels. Subjects on a statin at Screening will switch from their current statin to an equivalent intensity dose of rosuvastatin at Week 2 and will be dispensed additional rosuvastatin at Week 48 and continue through Week 54 (or Week 58 if LDL-C follow-up is needed).

[v] For subjects who were statin experienced at Baseline, medication compliance will be assessed at Week 54 only.

[w] All subjects will be assessed at Weeks 49 and 54 to confirm their LDL-C levels are decreasing to near baseline, at which point, no additional follow-up is needed. Subjects who do not meet LDL-C decrease criteria at Week 54 will have an additional 4-week follow-up visit at Week 58 to confirm their LDL-C has returned to near baseline.

[x] ONLY for subjects who were identified at Week 49 as needing re-assessment of LDL-C at Week 54, the third-party Medical Monitor will evaluate LDL-C results to assess the need to schedule a 4-week LDL-C safety follow-up visit (Study Week 58) to confirm their LDL-C value has returned to near baseline.

[y] For EW patients only, the last, on-treatment ELF values at the visit prior to the EW visit will also be measured, in addition to the EW visit. This measurement will be done using the banked serum samples for the Exploratory Biomarker.

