8.2.12. Week 48 / Early Withdrawal (End of Treatment) Procedures

Subjects will report to this visit fasted and not dosed with aldafermin.

The following procedures will be performed at the Week 48/Early Withdrawal visit:

Pre-dose:

- Measure body weight, BMI, and waist circumference
- Conduct physical examination and RUQ pain assessment with NRS
- Obtain 12-lead ECG (after subject has been supine for at least 5 minutes)

- Measure vital signs (including temperature, respiratory rate, and seated blood pressure and pulse)
- Conduct Chronic Liver Disease Questionnaire for NASH (CLDQ-NASH)
- Obtain FibroScan® scores (for transient elastography, VCTE™ and steatosis by ultrasound attenuation rate CAP™), where available
- Obtain an ultrasound liver for routine HCC surveillance
- Undergo a liver biopsy procedure to obtain new tissue
- Record concomitant medications
- Record AEs
- Obtain 10-hour fasted clinical laboratory samples for the following:
 - Chemistry
 - CBC
 - HbA1c
 - [REDACTED]
 - Insulin level
 - HOMA-IR calculation
 - INR
 - AFP
 - Serum pregnancy test (all female subjects of childbearing potential)
 - Lipid panel
 - Lipoprotein particles
 - Lipase
 - C4
 - Serum bile acids
 - PK
 - ADAs
 - NAbs
 - ELF panel
 - Pro-C3
 - Pro-C3X
 - CTX-III
 - C3M
 - Exploratory Plasma biomarker #1

- Exploratory Plasma biomarker #2
- Exploratory Serum biomarker #3

Results for ALT, AST, Total Cholesterol, LDL, HDL, and triglycerides are blinded to the site and sponsor.

Obtain urine sample:

- Urinalysis
- Urine drug screen

In-clinic dosing:

- Collect old aldafermin study drug kit and diary and conduct reconciliation
- Collect old rosuvastatin bottle and diary and conduct reconciliation
- Re-dispense rosuvastatin study drug and diary (only for subjects who were statin experienced at Baseline). Remind Subjects that they will be contacted in a few days regarding the delivery or pick up of their rosuvastatin/placebo drug bottles.
- Oversee subject's aldafermin study drug self-administration (from old kit) (not applicable for Early Withdrawal subjects)
- Perform LISSA evaluation.
- Obtain PK blood sample 4-hours post dose.
- Obtain C4 blood sample 4-hours post dose

Before clinic discharge:

(NOTE: PK sampling before clinic discharge is not applicable for Early Withdrawal subjects; however, Early Withdrawal subjects should be scheduled for a 6-week Follow-up visit.)

- Schedule subject for Week 49 Post-Treatment Response Visit

Lipid Lowering Therapy Assessment:

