8.3.17. Lipid Lowering Therapy Assessment

LDL-C will be evaluated at all study visits beginning at Week 2 for possible increases in lipid levels associated with aldafermin administration. Rosuvastatin will be used to manage cholesterol levels and initiated if protocol-defined lipid management criteria are met.

Rosuvastatin and matched placebo are over-encapsulated and provided in multi-capsule bottles ([Section 6.2.1.2](#)). Initiation and ongoing dose adjustments of rosuvastatin will be managed by a third-party Medical Monitor who is blinded to treatment assignment but unblinded to LDL-C values and related safety laboratory results. Rosuvastatin dose changes will be managed through the IxRS. Lipid levels and titration recommendations will be blinded to the sponsor, sponsor's Medical Monitor, investigators, subjects, and site. Initiation and dose adjustments will be determined by the lipid levels collected at Week 2 through Week 54, with lipid levels at Day 1 serving as baseline. LDL-C samples will be analyzed and reported to the third-party Medical Monitor. A kit containing rosuvastatin or matched placebo bottles will be assigned as instructed through the IxRS system and based on subjects LDL-C level assessment at each study visit from Week 2 through Week 42 (statin-naïve) or Week 48 (statin-experienced), and will be delivered to subjects via a courier service vendor ([Section 6.1.3.1](#)). The site will communicate to the subject the assigned bottle(s) and dosing should be immediately initiated.

Group A

Statin-experienced subjects (definition from Exclusion Criteria 9b) will be switched to an equivalent intensity rosuvastatin dose (high intensity dose – 20 mg rosuvastatin, moderate intensity dose – 10 mg rosuvastatin, low intensity dose – 5 mg rosuvastatin). For subjects who are self-identified Asians, the high intensity rosuvastatin dose is 10 mg, and the moderate intensity rosuvastatin dose is 5 mg. The treatment goal for this group of statin-experienced subjects is LDL-C level of ≤ 70 mg/dL (1.8 mmol/L) or $\geq 50\%$ LDL-C reduction from the Week 2 level, starting at Week 6.

Group B

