8.4. Safety and Other Assessments

8.4.1. Definition of Adverse Events

An AE is defined as any untoward medical occurrence in a patient or clinical investigational subject who has been administered a pharmaceutical product that does not necessarily have a causal relationship with this treatment. A TEAE is an AE that is reported after a dose of study drug.

AEs are all:

- unfavorable changes in general condition
- subjective or objective signs/symptoms
- concomitant diseases or accidents
- clinically relevant adverse changes in laboratory parameters observed in a participant in the course of a clinical study

AEs comprise all disturbances of general health status, subjective and objective disease symptoms (including laboratory abnormalities), and accidents observed in the context of a clinical trial, irrespective of a possible causal relationship with the administration of the trial substance. Events occurring in the framework of a clinical trial during drug-free, and post-treatment periods, or under placebo, are also to be designated as AEs.

All AEs, whether volunteered, elicited, or noted on physical examination, will be recorded throughout the study (i.e., from screening until EOS).

Subjects will be queried for resolution of ongoing AEs or until any unresolved AEs are judged by the PI to have stabilized or if lost to follow-up. Resolution of all AEs will be promptly documented by the clinic in the subject's CRF.

Any pregnancy diagnosed during the study must be reported immediately to the investigator and sponsor, including pregnancy in female partners of male subjects. The pregnancy will be followed to term and/or outcome and this outcome must be reported to the sponsor.

Pregnancy, in and of itself, is not regarded as an AE or SAE unless the birth results in a congenital anomaly/birth defect or there is suspicion that the study treatment may have interfered with the effectiveness of a contraceptive medication or method.

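### Required birth control and pregnancy testing stop at Week 54, although study rosuvastatin may continue to Week 58

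*Protocol*

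**What the plan says.** Inclusion criterion 12 (Section 5.1 and synopsis) requires birth control from Screening to End of Study and gives End of Study as Week 54. Table 8 note [m] schedules urine pregnancy tests through End of Study. Section 8.2.14, headed as the Week 54 End of Study visit, lists the last one.

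Rosuvastatin follows a different calendar. Note [u] says that subjects on a statin at Screening "will be dispensed additional rosuvastatin at Week 48 and continue through Week 54 (or Week 58 if LDL-C follow-up is needed". The text of 8.1 and of 4.1 also permits statin treatment up to Week 58. Section 8.2.14 puts the end of participation at Week 58 for subjects who need the extra lipid visit. Section 8.2.15 lists three items for that visit: concomitant medications, adverse events and a fasting lipid panel.

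On pregnancy itself, the mandatory discontinuation grounds in 7.2 include "that significantly affect subject safety or study integrity, development of pregnancy". Section 8.4.1 requires any pregnancy to be reported immediately to the investigator and sponsor and followed to its outcome.

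**The concern.** Rosuvastatin is supplied by the sponsor and sits under Study Treatment (6.1.3). The protocol sets contraception and testing rules for women of childbearing potential and removes a subject who becomes pregnant. Those rules should last as long as study drug may be taken. Week 54 is six weeks after the last aldafermin dose at Week 48, so it is a natural end date for aldafermin. It is not the end date for rosuvastatin in subjects who go on to Week 58.

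What is at stake is patient safety in a small subset: possible exposure of an unrecognised pregnancy to study-supplied drug. No efficacy result depends on it.

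**Working it through.** The inputs are:

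- End of required birth control: Week 54 (inclusion criterion 12).
- Last scheduled urine pregnancy test: Week 54 (note [m]; 8.2.14).
- Latest permitted study rosuvastatin: Week 58 (4.1; 8.1; note [u]).
- End of participation for these subjects: Week 58 (8.2.14).
- Pregnancy tests listed at Week 58: 0 (8.2.15).
- Visit window: ±3 days at Week 54 and ±3 days at Week 58 (8.1; note [b]).

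**Length of the uncovered interval**

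- Nominal: (58 − 54) × 7 = 28 days.
- Shortest (Week 54 visit 3 days late, Week 58 visit 3 days early): 28 − 3 − 3 = 22 days.
- Longest (Week 54 visit 3 days early, Week 58 visit 3 days late): 28 + 3 + 3 = 34 days.

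**Who can be in it**

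Under 8.3.17, kits are assigned up to Week 42 for statin-naïve subjects and up to Week 48 for statin-experienced subjects. Note [u] likewise continues supply after Week 48 only for those on a statin at Screening. The extra visit applies to subjects whose Week 54 LDL-C is neither within 15 mg/dL of Day 1 nor at the protocol goal (8.1). The affected women must therefore be of childbearing potential, statin-experienced, and outside the LDL-C criteria at Week 54. The protocol gives no count for any of these, so no frequency can be derived.

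**Is exposure in the interval certain?**

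No. Section 8.2.14 collects old rosuvastatin bottles at Week 54 and lists no new supply, while 8.1 and note [u] allow treatment to continue. The 22 to 34 days are permitted exposure, not demonstrated exposure.

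None of this depends on where marks fall in the Table 8 grid. It rests on section text and table notes.

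**The case against.** The best case against the point has three parts.

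1. The women concerned were already taking a prescribed statin before the trial, so the trial adds little new exposure.
2. They have a pregnancy test at Week 54, and supply after that visit is doubtful.
3. No visible text says that rosuvastatin is harmful in pregnancy. The package insert (Appendix 5) is only linked, and the Appendix 4 algorithm is not visible. Criterion 12 does refer to the risk period of the study treatments, but there it defines when abstinence counts as highly effective and sets no risk period for rosuvastatin.

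All of this stands, and it limits the point to a modest one. It does not remove the mismatch: the protocol sets its own safeguards and permits study drug beyond their end.

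A reader might infer something stronger: that a subject withdrawn for pregnancy would be handed more statin. The combined Week 48/Early Withdrawal list in 8.2.12 says "Re-dispense rosuvastatin study drug and diary (only for subjects who were statin experienced at Baseline" and makes no exception for early withdrawal, whereas the aldafermin dosing item does. Section 7.2 has "Notification of discontinuation will be made immediately to the sponsor Medical Monitor or designee", while under 8.3.17 "Initiation and ongoing dose adjustments of rosuvastatin will be managed by a third-party Medical Monitor", and 8.4.1 says "Pregnancy, in and of itself, is not regarded as an AE or SAE". The documents still do not support that reading. Although an earlier sentence in 7.2 is permissive, the later one makes discontinuation for pregnancy mandatory, and leaving the study ordinarily ends study treatment. Section 8.4.1 adds immediate reporting. Not naming rosuvastatin is missing detail, not an unsafe instruction.

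Nor is there a firm conflict between 8.2.12 and Table 8. The dispensing row has one shared column for Week 48 and Early Withdrawal. Note [u] requires dispensing at Week 48, so a blank there cannot be read as a rule for early withdrawal. Several other rows in the available text of the table (HbA1c, serum bile acids, lipase, ELF) also do not line up with the visit lists, so cell positions carry no weight.

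**Conclusion.** The point holds in a narrow form. For women of childbearing potential who continue study rosuvastatin after Week 54, the protocol leaves a nominal 28 days, 22 to 34 with visit windows, with no required birth control and no scheduled pregnancy test.

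This assumes that 8.1 and note [u] are applied as written and that such subjects actually have drug to take after Week 54, which 8.2.14 leaves open. It also assumes that neither the Appendix 4 algorithm nor the linked insert already imposes a later end date. The subset is small and no event rate is claimed. A cheap correction is worth making on safety grounds.

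**What to change.** For female subjects of childbearing potential who stay on study rosuvastatin after Week 54:

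- In inclusion criterion 12, extend required birth control to Week 58 or to the last rosuvastatin dose.
- In Table 8, note [m] and 8.2.15, add a urine pregnancy test at the existing Week 58 visit.

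The cost is wording edits at the next amendment, one urine test, and four more weeks of contraception in a small subset.

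As an optional clarification, state in 7.2 and 8.2.12 that rosuvastatin is not re-dispensed to a subject withdrawn for pregnancy and that the third-party Medical Monitor is informed.

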8. STUDY PROCEDURES

8.1. Schedule of Study Procedures

The Schedule of Study Procedures is shown in [Table 8](#). The visits should occur as close to the intended dates as possible. However, there is an acceptable ± 3 -day window from Week 2 through Week 6, and Week 54 (Week 58 if needed). Visit window from Weeks 12 through 48 is ± 7 days. Visit window for Week 49 is $+3$ days.

Subjects attending any visits out of windows from Day 1 to Week 48/Early Withdrawal (EOT) visit should be brought back into compliance with the overall study visit schedule as soon as possible thereafter.

The PI has discretion to repeat assessments if he/she believes the results are erroneous or to rule out worsening of liver disease (Exclusion #7) for Day -56 and Day -42 visits. Repeat assessments must be conducted within the 8-week Screening Period. The screening window may be increased up to 16 weeks (112 days) to obtain all screening assessments, with Medical Monitor approval. Only assessments that need to be repeated should be done rather than a full re-screening of the subject. The results of the repeat testing will be used for evaluation.

All subjects will be assessed at Weeks 49 and 54 to confirm their LDL-C levels have returned to near baseline. At that point, no additional follow-up will be performed.

Subjects who do not meet criteria at Week 54 (Day 1 levels within 15 mg/dL or at the protocol-defined LDL-C goal) will have an additional 4-week follow-up visit at Week 58 to confirm that their LDL-C level returned to near baseline or at the protocol-defined LDL-C goal. Subjects may remain on over-encapsulated rosuvastatin through Week 58.

All subjects will have pre-dose PK blood collection on all treatment visits as well as 4-hours post-dose on Day 1, Week 24, and Week 48.

All subjects will be offered the opportunity to participate in a PK sub-study, which will involve a few additional procedures, including blood draws (i.e., on Day 1 and Week 48 at pre-dose, and post-dose at 0.5, 1, 2, 4, 6, 8, 12, and 24 hours). Reference [Table 8](#) for more details.

Table 8. Schedule of Assessments

| Study Procedure | Screening [a] | | Treatment Visits | | | | | | | | | | Follow-up | | LDL-C monitor |
|--|------------------|---------------|------------------|------|------|-------|-------|-------|-------|-------|-------|----------------------|-----------|----------------|------------------|
| | D-56 | D-42 to -1 | Day 1 | Wk 2 | Wk 6 | Wk 12 | Wk 18 | Wk 24 | Wk 30 | Wk 36 | Wk 42 | Wk 48/EW (EOT) | Wk 49 | Wk 54 (EOS) | |
| | | | | | | | | | | | | | | Wk 58 [x] | |
| Visit Window (Days) [b] | | | | ± 3 | ± 3 | ± 7 | ± 7 | ± 7 | ± 7 | ± 7 | ± 7 | ± 7 | +3 | ± 3 | ± 3 |
| Informed consent | X | | | | | | | | | | | | | | |
| Inclusion/exclusion criteria | X | | X | | | | | | | | | | | | |
| Demographics | X | | | | | | | | | | | | | | |
| Medical history | X | | | | | | | | | | | | | | |
| Smoking status | X | | | | | | | | | | | | | | |
| Height | X | | | | | | | | | | | | | | |
| Alcohol Consumption [c] | X | | | | | | | | | | | | | | |
| Body weight [d], BMI [e], waist circumference | X | | X | | | | X | | X | X | | X | | X | |
| Physical exam and RUQ pain assessment | X | | X | | X | X | X | X | X | X | X | X | X | X | |
| 12-lead ECG | X | | X | | | | X | | | X | | X | | X | |
| Vital signs | X | | X | X | X | X | X | X | X | X | X | X | X | X | |
| Chronic Liver Disease Questionnaire-NASH (CLDQ-NASH) | | X | | | | | X | | | | | X | | X | |
| Gadolinium-enhanced MRI, CT, or ultrasound for HCC screening [f] | | X | | | | | | | | | | | | | |
| Ultrasound scan (local read) for HCC surveillance | | | | | | | | X | | | | X | | | |
| FibroScan® (VCTE™)/ (CAP™) [g] | X | | | | | | | X | | | | X | | | |
| EGD | | X | | | | | | | | | | | | | |
| Liver biopsy [h] | | X | | | | | | | | | | X | | | |
| Randomization | | | X | | | | | | | | | | | | |
| Prior and concomitant medications | X | X | X | X | X | X | X | X | X | X | X | X | X | X | |

| Study Procedure | Screening [a] | | Treatment Visits | | | | | | | | | | Follow-up | | LDL-C monitor |
|---|------------------|---------------|------------------|------------------|------------------|------------------|------------------|------------------|------------------|------------------|------------------|----------------------|------------------|------------------|------------------|
| | D-56 | D-42 to -1 | Day 1 | Wk 2 | Wk 6 | Wk 12 | Wk 18 | Wk 24 | Wk 30 | Wk 36 | Wk 42 | Wk 48/EW (EOT) | Wk 49 | Wk 54 (EOS) | Wk 58 [x] |
| | | | | | | | | | | | | | | | |
| Visit Window (Days) ^[b] | | | | ± 3 | ± 3 | ± 7 | ± 7 | ± 7 | ± 7 | ± 7 | ± 7 | ± 7 | +3 | ± 3 | ± 3 |
| Adverse event (AE) evaluations ^[i] | X | X | X | X | X | X | X | X | X | X | X | X | X | X | X |
| LISSA evaluations | | | X | X | X | X | X | X | X | X | X | X | | | |
| Chemistry, including creatine kinase (fasted ≥ 10 hrs) ^[i,k] | X | | X | X | X | X | X | X | X | X | X | X | X | X | |
| Laboratory assessments for worsening liver disease ^[l] | | X | | | | | | | | | | | | | |
| Complete blood count (CBC) | X | | X | X | X | X | X | X | X | X | X | X | X | X | |
| HbA1c | X | | X | | | | | | | | | | X | | X |
| Insulin level and HOMA-IR | X | | X | | | | | X | | | | X | | X | |
| | | | █ | | | | | | | | | █ | | █ | |
| International Normalized Ratio (INR) | X | X | X | X | X | X | X | X | X | X | X | X | X | X | |
| Alpha fetoprotein (AFP) | X | | | | | | | X | | | | | X | X | |
| Pregnancy test ^[m] | X | X | X | X | X | X | X | X | X | X | X | X | X | X | |
| Hepatitis and HIV Ab screen | X | | | | | | | | | | | | | | |
| Urinalysis (UA) | X | | X | | | | | X | | | | | X | | X |
| Urine drug screen ^[n] | X | | X | | | | | X | | | | | X | | |
| PEth alcohol screen | X | | | | | | | | | | | | | | |
| Fasting lipid panel | X | | X ^[o] | X ^[o] | X ^[o] | X |
| Lipoprotein particles | | | X | X | X | X | X | X | X | X | X | X | | | X |
| Lipase | | | X | | X | X | | X | | X | | X | | | X |
| Serum bile acids ^[o] | | | X | | | | | | | | | | X | | |
| C4 ^[p] | | | X | X | X | X | X | X | X | X | X | X | | | |
| PK blood samples ^[q,r] | | | X | X | X | X | X | X | X | X | X | X | | | |
| Anti-drug antibodies (ADAs) | | | X | X | X | X | | X | | X | | X | | | X |
| Neutralizing antibodies (NAbS) | | | X | X | X | X | | X | | X | | X | | | X |
| ELF Panel | | | X | | | | | X | | | | X ^[r] | | | X |
| Pro-C3 | | | X | | | | | X | | | | X | | | X |
| Pro-C3X | | | X | | | | | X | | | | X | | | X |

| Study Procedure | Screening ^[a] | | Treatment Visits | | | | | | | | | Follow-up | | LDL-C monitor | |
|---|--------------------------|------------|------------------|------|------|-------|-------|-------|-------|-------|-------|----------------|------------------|---------------------|----------------------|
| | D-56 | D-42 to -1 | Day 1 | Wk 2 | Wk 6 | Wk 12 | Wk 18 | Wk 24 | Wk 30 | Wk 36 | Wk 42 | Wk 48/EW (EOT) | Wk 49 | Wk 54 (EOS) | Wk 58 ^[x] |
| | | | | | | | | | | | | | | | |
| Visit Window (Days) ^[b] | | | | ± 3 | ± 3 | ± 7 | ± 7 | ± 7 | ± 7 | ± 7 | ± 7 | ± 7 | +3 | ± 3 | ± 3 |
| CTX-III | | | X | | | | | X | | | | X | | X | |
| C3M | | | X | | | | | X | | | | X | | X | |
| PNPLA3/Genetic Biomarkers ^[s] | | | X | | | | | | | | | | | | |
| Exploratory Biomarker 1, 2, 3 | | | X | X | X | X | X | X | X | X | X | X | X | X | |
| Aldafermin/placebo in clinic self-administration ^[t] | | | X | X | X | X | X | X | X | X | X | X | | | |
| Dispense aldafermin and diary | | | X | X | X | X | X | X | X | X | X | | | | |
| Dispense rosuvastatin ^[u] and diary | | | | X | X | X | X | X | X | X | X | | | | |
| Medication compliance | | | | X | X | X | X | X | X | X | X | | | X ^[v] | |
| Lipid management | | | | X | X | X | X | X | X | X | X | X | X ^[w] | X ^[w, x] | |

^[a] There must be a minimum of 14 days (2 weeks) between Day -56 and Day -42 Screening Visits to allow for adequate separation of liver function testing prior to randomization in order to evaluate worsening liver function, per Exclusion #7. If liver function tests are repeated to verify eligibility criteria have been met, there must be a minimum of 14 days (2 weeks) between the Day -42 visit and any unscheduled visit. The screening window may be increased up to 16 weeks (112 days) to obtain all screening assessments, with Medical Monitor approval.

^[b] Acceptable window from Week 2 through Week 6, and Week 54 (Week 58 if needed) is ±3-days. Visit window from Weeks 12 through 48 is ± 7 days. Visit window for Week 49 is +3 days.

^[c] During screening, sites will complete; i) AUDIT-C alcohol consumption questionnaire and, ii) document subject- reported alcohol consumption to confirm whether amounts are within protocol defined limits, and iii) PEth level ≥200 ng/mL (refer to exclusion criteria #18, 20).

^[d] Subjects should maintain their normal level of physical activity, diet, and lifestyle throughout the entire study.

^[e] BMI will be calculated with height obtained at Screening.

^[f] Gadolinium-enhanced MRI and multiphasic CT imaging must not have any nodules with LI-RADS ≥2. If nodules/lesions discovered on ultrasound that have not been previously defined by MRI or CT as clearly benign or LI-RADS <2, follow-up imaging with MRI or CT must be conducted for eligibility.

^[g] FibroScan® (transient elastography (VCTE™) or ultrasound attenuation rate (CAP™) should be collected at Screening Day -56, Week 24, and Week 48 at sites with available technology.

^[h] All subjects are required to have a liver biopsy result at Screening and additional liver biopsy at Week 48. A Screening liver biopsy will be performed only in subjects who do not have a qualified historical biopsy available for central pathology evaluation. The Week 48 biopsy should be obtained before the last dose of aldafermin with a visit window of 7 days prior to the end of treatment period.

^[i] Adverse events will be monitored and recorded from subject signing informed consent through follow-up.

^[j] Serum chemistry will include ALT, AST, ALP, bicarbonate, bilirubin (direct and total), BUN, calcium, chloride, creatinine, CK, GGT, glucose, HDL, LDL, phosphate, potassium, proteins (albumin, total protein), sodium, total cholesterol, and TG. Lab results for ALT, AST, total cholesterol, LDL, HDL, and triglycerides are blinded to the site and sponsor from Week 2 onward.

[k] Creatine kinase will be collected at all time points as serum chemistry.

[l] Per Exclusion #7, total bilirubin, AST, ALT, ALP

[m] A serum pregnancy test will be performed on all female subjects of childbearing potential at Day -56 Screening visit, Week 24, and Week 48. A urine pregnancy test will be performed on all female subjects of childbearing potential at all study visits through EOS.

[n] Urine drug and alcohol tests may be repeated during treatment for subjects suspected of excessive alcohol intake or to rule out association with a safety event.

[o] Serum bile acids will be collected pre-dose Day 1 and Week 48/early withdrawal.

[p] C4 will be collected pre-dose on Day 1 and Weeks 2, 6, 12, 18, 24, 30, 36, 42, 48 and 4-h post dose on Days 1, Weeks 24, and 48. In addition, for subjects participating in the optional PK sub-study, additional C4 will be tested at the same time points as the PK blood sample collections: Day 1 and Week 48 at pre-dose, and post-dose at 0.5, 1, 2, 4, 6, 8, 12, and 24 hours. The window for sample collection for the pre-dose through 4 hours is ± 5 minutes, 6-12-hour time points is ± 30 minutes. The window for sample collection for the 24-hour time points is -2 hours.

[q] PK blood samples will be collected in all subjects before dosing themselves in the clinic (pre-dose) on Day 1, Weeks 2, 6, 12, 18, 24, 30, 36, 42, and 48 and 4-hours post-dose on Day 1, Week 24 and Week 48.

[r] For subjects participating in the optional PK sub-study, blood samples will be collected when the subjects dose themselves in the clinic on Day 1 and Week 48 at pre-dose, and post-dose at 0.5, 1, 2, 4, 6, 8, 12, and 24 hours. The window for sample collection for the pre-dose through 4 hours is ± 5 minutes, 6-12-hour time points is ± 30 minutes. The window for sample collection for the 24-hour time points is -2 hours.

[s] A single buccal swab sample for PNPLA3/other genetic biomarkers will be collected pre-dose on Day 1.

[t] Subjects will be instructed to self-inject aldafermin/placebo in the abdomen at a similar time each day. Subjects will not self-inject aldafermin/placebo at home on clinic visit day.

[u] Rosuvastatin will be dispensed at Weeks 2, 6, 12, 18, 24, 30, 36, and 42 visits and subjects will be provided further dosing instruction based on their ASCVD risk assessment, prior statin history (statin naïve or statin experienced), and LDL-C levels or LDL reduction levels. Subjects on a statin at Screening will switch from their current statin to an equivalent intensity dose of rosuvastatin at Week 2 and will be dispensed additional rosuvastatin at Week 48 and continue through Week 54 (or Week 58 if LDL-C follow-up is needed).

[v] For subjects who were statin experienced at Baseline, medication compliance will be assessed at Week 54 only.

[w] All subjects will be assessed at Weeks 49 and 54 to confirm their LDL-C levels are decreasing to near baseline, at which point, no additional follow-up is needed. Subjects who do not meet LDL-C decrease criteria at Week 54 will have an additional 4-week follow-up visit at Week 58 to confirm their LDL-C has returned to near baseline.

[x] ONLY for subjects who were identified at Week 49 as needing re-assessment of LDL-C at Week 54, the third-party Medical Monitor will evaluate LDL-C results to assess the need to schedule a 4-week LDL-C safety follow-up visit (Study Week 58) to confirm their LDL-C value has returned to near baseline.

[y] For EW patients only, the last, on-treatment ELF values at the visit prior to the EW visit will also be measured, in addition to the EW visit. This measurement will be done using the banked serum samples for the Exploratory Biomarker.

